1. PROTOCOL SYNOPSIS FOR STUDY 204682

Rationale

Albiglutide is a novel analogue of glucagon-like peptide-1 (GLP-1) with a sufficiently long half-life to permit once a week injection. Albiglutide has been developed for the treatment of type 2 diabetes mellitus (T2DM) as an adjunct to diet and exercise, as monotherapy, or in combination with existing therapies and has been approved by the US Food and Drug Administration (FDA), the European Medicines Agency (EMA) and other regulatory agencies.

This open-label extension (Study 204682) to Study 200952 will provide additional safety, tolerability and immunogenicity data for the albiglutide liquid drug product.

Objective(s)/Endpoint(s)

Primary	

 To provide extended safety, tolerability and immunogenicity data for the albiglutide liquid drug product. 	
 Adverse events (AEs) and serious adverse events (SAEs), physical examinations, clinical laboratory evaluations, vital signs, and 12-lead electrocardiograms (ECGs). Anti-albiglutide antibody production over time.
Exploratory	

 To provide safety and tolerability data on the transition from albiglutide lyophilized to liquid drug product. To further evaluate the PD effect of albiglutide liquid drug product on HbA1c and FPG. To gain additional patient experience with the albiglutide liquid drug product via auto-injector. 	
 AEs and SAEs, physical examinations, clinical laboratory evaluations, vital signs, and 12-lead ECGs. Anti-albiglutide antibody production over time. Change from baseline in HbA1c and FPG at Week 52. Exploring patient experience and satisfaction.

Overall Design

- This is a 26 week, open-label, single group, multicenter, extension study to Study 200952. This extension study will provide extended safety, tolerability and immunogenicity data for the albiglutide liquid drug product.
- This extension study will recruit subjects who have completed Study 200952 and satisfy all inclusion/exclusion criteria.

- In addition to receiving albiglutide liquid drug product, subjects will continue on their current regimen of diet and exercise or stable dose of background metformin (if applicable).

Treatment Arms and Duration

- This extension study will comprise 2 study periods: treatment (26 weeks) and post-treatment follow-up (8 weeks).
- All subjects will receive 50 mg albiglutide liquid drug product via auto-injector.
- Study treatment will be administered once weekly by s.c. injection in the abdomen, thigh, or upper arm.

Type and Number of Subjects

- This extension study will recruit subjects who have completed Study 200952 and satisfy all inclusion/exclusion criteria.
- A maximum of 300 subjects will be eligible to take part in this extension study.

Analysis

Primary analyses:

The overall general safety and tolerability of albiglutide liquid drug product will be evaluated in tabular and/or graphical format and summarized descriptively.

The evaluation of the safety and tolerability as assessed by immunogenicity of albiglutide liquid drug product will be provided by reporting descriptive statistics.

Exploratory analyses:

The overall general safety and tolerability of albiglutide liquid drug product for subjects who are randomized to albiglutide lyophilized drug product in Study 200952 and transition to albiglutide liquid drug product in this extension study will be evaluated in tabular and/or graphical format and summarized descriptively.

The safety and tolerability as assessed by immunogenicity for the subject who transition to albiglutide liquid drug product in the extension study will be summarized descriptively.

HbA1c and FPG change from baseline will be summarized descriptively and/or graphically.

Patient experience and satisfaction with the auto-injector and albiglutide liquid product as measured by a self completed patient exit questionnaire at the end of treatment visit (Week 52) will be assessed using summary statistics.

2. INTRODUCTION

Albiglutide is a novel analogue of GLP-1 with a sufficiently long half-life to permit once a week injection. Albiglutide has been developed for the treatment of T2DM as an adjunct to diet and exercise, as monotherapy, or in combination with existing therapies and has been approved by the US FDA, the EMA and other regulatory agencies.

2.1. Study Rationale

Study 200952, a randomized, double-blind, repeat-dose study in subjects with T2DM will determine if there are any clinically relevant differences between albiglutide liquid drug product and albiglutide lyophilized drug product with respect to safety, tolerability and pharmacodynamic (PD) response. This open-label extension (Study 204682) to Study 200952 will provide additional safety, tolerability and immunogenicity data for the albiglutide liquid drug product.

3. OBJECTIVE(S) AND ENDPOINT(S)

Objectives	Endpoints
Primary	

 To provide extended safety, tolerability and immunogenicity data for the albiglutide liquid drug product. 	
 AEs and SAEs, physical examinations, clinical laboratory evaluations, vital signs, and 12-lead ECGs. Anti-albiglutide antibody production over time.
Exploratory	

 To provide safety and tolerability data on the transition from albiglutide lyophilized to liquid drug product. To further evaluate the PD effect of albiglutide liquid drug product on HbA_{1c} and FPG. To gain additional patient experience with the albiglutide liquid drug product via auto-injector. 	
 AEs and SAEs, physical examinations, clinical laboratory evaluations, vital signs, and 12-lead ECGs. Anti-albiglutide antibody production over time. Change from baseline in HbA_{1c} and FPG at Week 52. Exploring patient experience and satisfaction.

[figure not shown]
4. STUDY DESIGN

4.1. Overall Design

- This is a 26 week, open-label, single group, multicenter, extension study to Study 200952. This extension study will provide extended safety, tolerability and immunogenicity data for the albiglutide liquid drug product.

- This extension study will recruit subjects who have completed Study 200952 and satisfy all inclusion/exclusion criteria (Section 5).
- In addition to receiving albiglutide liquid drug product, subjects will continue on their current regimen of diet and exercise or stable dose of background metformin (if applicable).
- An overview of the study design is provided in Figure 1

Figure 1 Study Schematic

4.2. Treatment Arms and Duration

- This extension study will comprise 2 study periods (Figure 1): treatment (26 weeks) and post-treatment follow-up (8 weeks).
- All subjects will receive 50 mg albiglutide liquid drug product via auto-injector.
- Study treatment will be administered once weekly by s.c. injection in the abdomen, thigh, or upper arm.
- The first dose of study treatment will be administered by the subject during the clinic visit (Visit 1, Week 26) with supervision from clinic staff. All further doses of study treatment will be self-administered by the subject.
- During the study, any potential events of pancreatitis will be adjudicated by an independent pancreatitis adjudication committee (PAC) (Section 10.8).

4.3. Type and Number of Subjects

- This extension study will recruit subjects who have completed Study 200952 and satisfy all inclusion/exclusion criteria (Section 5).
- Maximum of 300 subjects will be eligible to take part in this extension study.

4.4. Design Justification

This is an open-label, long term extension to Study 200952. All subjects may choose to continue in the extension study if eligible to participate. The selected 26 week extension

treatment duration should appropriately capture the continuation of the safety, tolerability and immunogenicity data for the albiglutide liquid drug product.

4.5. Dose Justification

Phase III studies confirmed the glycemic efficacy of both 30 mg and 50 mg doses of albiglutide lyophilized drug product, and both were generally well-tolerated. Although the 30 mg dose was effective at controlling glycemia for at least 2 years in many subjects with T2DM, an increase in dose to 50 mg weekly offered additional benefit without significant safety issues (See Investigator Brochure [IB] for further details).

In this extension study all subjects will receive 50 mg of albiglutide liquid drug product once weekly for 26 weeks.

4.6. Benefit:Risk Assessment

Albiglutide lyophilized drug product has been evaluated in an international program of studies involving over 4000 subject-years of exposure to albiglutide. The program included 8 well-controlled Phase III studies ranging in duration from 32 weeks to 3 years, and using both 30 mg and 50 mg once weekly dosing. This has permitted a thorough assessment of efficacy, safety, and tolerability in a population of subjects with T2DM that spanned newly diagnosed individuals treated with diet and exercise alone through to subjects on background oral monotherapy, oral dual therapy, oral triple therapy, and basal insulin.

Summaries of findings from both clinical and non-clinical studies conducted with the albiglutide (GSK716155) lyophilized drug product can be found in the IB and in the product labeling for those countries where marketing authorization has been granted.

The following sections outline the risk assessment and mitigation strategy for this protocol which would apply to the new liquid drug product in development.

A detailed description of the characteristics of the liquid drug product in the auto-injector device and results of nonclinical studies with this investigational formulation are presented in the IB Supplement.

Summary characteristics of the liquid drug product are shown in [Table 1](#).

Table 1 Composition of Albiglutide (Liquid for Injection, 30 mg and 50 mg)

Component	Liquid Albiglutide	
	30 mg dose	50 mg dose
Injector type	Pre-filled syringe with auto-injector	
Final formulation pH	5.9	
Final albiglutide concentration	50 mg/mL	
Injection volume	0.6 mL	1.0 mL

Stability data thus far suggest that the same product-related variants/impurity profiles are present in the liquid and commercial lyophilized drug products when stored at the

recommended conditions. Based on the current understanding of albiglutide degradation pathways and clinical outcomes from exposure to variants/impurities, similar pharmacokinetic (PK), PD, and clinical comparability between the liquid drug product and the lyophilized drug product is expected.

4.6.1. Risk Assessment

Key identified and potential risks associated with administration of albiglutide in this study and mitigation strategies included in the protocol are summarized in [Table 2](#). At this stage, the risk profile and associated pharmacovigilance and mitigation strategies are considered generally applicable to both the approved lyophilized drug product and the investigational liquid drug product. No risks specific to the liquid drug product have been identified in non-clinical studies to date. Mitigation strategies for this study have been incorporated for those risks (e.g., immunogenicity, injection site reactions) where a potential for differences between the liquid and lyophilized drug products has been recognized.

Please also refer to the IB and any supplements as well as the complete Guidance for the Investigator and local approved product labeling.

Table 2 Risk Assessment for Albiglutide (GSK716155)

Potential Risk of Clinical Significance	Summary of Data/Rationale for Risk	Mitigation Strategy
Investigational Product (IP) (albiglutide [GSK716155]) Identified Risks		
Pancreatitis	
Acute pancreatitis has been reported in association with albiglutide and other GLP-1 receptor agonists in clinical trials and during postmarketing experience.
 
Albiglutide has not been studied in subjects with a history of pancreatitis to determine whether they are at increased risk for pancreatitis.
	
Subjects with a history of acute or chronic pancreatitis were excluded from entering study 200952.
 
Subjects will be informed of the characteristic symptom of pancreatitis: persistent severe abdominal pain. If pancreatitis is suspected, albiglutide should be promptly discontinued and if pancreatitis is confirmed, study treatment will not be restarted (see Section 5.4).
 
Risk communication via guidance for investigators (see Section 6 of the IB) and informed consent form for subjects.

Gastrointestinal (GI) events.	
Albiglutide has not been studied in subjects with severe GI disease, including severe gastroparesis.
 
Use of albiglutide can be associated with GI side effects such as diarrhea, nausea, and vomiting.
	
Subjects with severe gastroparesis were excluded from entering study 200952.
 
Subjects with a history of significant GI surgery that in the opinion of the investigator is likely to significantly affect upper GI or pancreatic function were excluded from entering study 200952
 
Risk communication via guidance for investigators (see Section 6 of the IB) and informed consent form for subjects.

Hypoglycemia.	
Albiglutide's mechanism of action is associated with a low intrinsic risk of significant hypoglycemia when used as monotherapy or in combination with agents such as metformin which also have low intrinsic risk for significant hypoglycemia.
	
Subjects are neither allowed to use insulin nor insulin secretagogues during the study. Except as part of hyperglycemia rescue (see Section 5.3)
 
Risk communication via guidance for investigators (see Section 6 of the IB) and informed consent form for subjects.

Immunogenicity (e.g., including anti-drug antibodies, clinical sequelae of	
Hypersensitivity reactions are of potential concern with any injected protein and were reported rarely in the Phase III
	
Subjects with known allergy to any GLP-1 receptor agonist or excipients of albiglutide are excluded from entering

Potential Risk of Clinical Significance	Summary of Data/Rationale for Risk	Mitigation Strategy
antidrug antibodies, severe hypersensitivity reactions, and other potential immune-related adverse events)	
program with lyophilized albiglutide.
 
Risk assessment of the albiglutide molecule predicted low immunogenic potential, which was substantiated for the commercial lyophilized pen injector product in the registration program. Treatment-emergent anti-drug antibodies were detected in ~5% subjects over studies of up to 3 years duration and were generally transient, of low titer, and not neutralizing.
 
Subjects who tested positive for anti-albiglutide antibodies experienced a similar glycemic response (HbA1c and fasting plasma glucose) to those who did not test positive for antibodies. Other than ISRs (see below), the overall safety profile appeared similar among the subset of subjects who did and those who did not test positive for anti-albiglutide antibodies.
 
Changes in the propensity of the liquid drug product to form aggregates could have an impact on anti-drug antibody characteristics or immune related AE. However, the likelihood of clinically important changes in anti-drug antibody characteristics or immune related AEs with the albiglutide liquid drug product compared to the lyophilized product is considered low based on the absence of substantive qualitative differences between formulations.
	
study 200952
 
Subjects will be informed of the symptoms of severe hypersensitivity or allergy and be advised to seek medical assistance immediately.
 
The development of anti-albiglutide antibodies and of injection site reactions will be assessed as part of this study.

Injection site reactions (ISRs)	
Albiglutide injections may cause rash, erythema or itching and/or other reactions at the site of injection.
 
In the Phase III program with the lyophilized formulation, most subjects with ISRs did not test positive for anti-albiglutide antibodies. However, injection site reactions were reported more frequently among those who did test positive for anti-albiglutide antibodies (41% of the anti-drug antibody positive subjects reported one or more injection site reactions) than among those who were consistently antibody negative (14% of the antidrug antibody negative
	
Subjects will be advised that when injecting in the same region, to use a different injection site each week.
 
Risk communication via guidance for investigators (see Section 6 of the IB) and informed consent form for subjects.

Potential Risk of Clinical Significance	Summary of Data/Rationale for Risk	Mitigation Strategy
	
subjects reported one or more injection site reactions).
 
Overall, for lyophilized albiglutide, ISRs have not been associated with clinically significant sequelae; although they can be a tolerability issue and were the most common reason for withdrawal of study medication for subjects (approximately 2.0%) in the albiglutide group.
 
Differences between formulation characteristics (e.g. lower pH and larger volume for the 50 mg dose of the liquid drug product) may impact the injection site reaction profile.
	

Other adverse reactions (e.g., pneumonia, atrial fibrillation/atrial flutter, appendicitis, and hypersensitivity reactions)
	
In the Phase III program in T2DM, other possible albiglutide related adverse reactions were identified. These events occurred at a cumulative incidence <3% in studies up to 3 years in duration. These events were reported more frequently with albiglutide than comparators.
	
Subjects with a known allergy to albiglutide or any product components (including yeast and human albumin) were excluded from entering study 200952.
 
Risk communication via guidance for investigators (see Section 6 of the IB) and informed consent form for subjects.

Investigational Product (IP) (albiglutide [GSK716155]) Potential Risks
		

Thyroid C-cell tumors
	
GLP-1 receptor agonists, including albiglutide increase serum calcitonin in rodents and other GLP-1 receptor agonists are associated with thyroid C-cell focal hyperplasia and C-cell tumors in rodents. It is unknown whether GLP-1 receptor agonists are associated with thyroid C-cell tumors in humans, including medullary thyroid cancer (MTC).
	
Subjects with a personal or family history of MTC or subjects with Multiple Endocrine Neoplasia syndrome type 2 (MEN-2) were excluded from entering study 200952.
 
Subjects with treatment emergent thyroid nodules should be referred to a specialist for evaluation in accordance with local treatment guidelines. Routine monitoring of serum calcitonin is not recommended. However, if serum calcitonin is found to be elevated the subject should be referred to a specialist for further evaluation. If MTC or other thyroid C-cell neoplasia is diagnosed, study treatment will be discontinued (see Section 5.4).


Other malignant neoplasms
	
Theoretical concerns have been raised regarding use of incretin based therapies and other malignancies such as pancreatic cancer [Egan, 2014] and malignancy when used in combination with insulin based on hypotheses of
	
Subjects with a history of cancer were excluded from entering study 200952
 
Risk communication via guidance for investigators (see

Potential Risk of Clinical Significance	Summary of Data/Rationale for Risk	Mitigation Strategy
	biological plausibility [European Public Assessment Report, 2014], and hematological malignancies [FDA Summary Basis of Approval, 2014].	Section 6 of the IB) and informed consent form for subjects
Cardiovascular (CV) safety of antidiabetic therapy	
T2DM is associated with an elevated risk of CV disease. Global regulatory agencies require new antidiabetic therapies to demonstrate that the new therapy is not associated with an unacceptable increase in CV risk.
 
In the Phase III registration program, an independent Clinical Endpoint Committee prospectively adjudicated blinded CV events. The final CV meta-analysis showed no increased CV risk (MACE+ composed of CV death, myocardial infarction (MI), stroke, and hospitalization for unstable angina) with albiglutide versus all comparators (MACE+ hazard ratio = 1.00; 95% CI: 0.68, 1.49).
	
Subjects with clinically significant CV and/or cerebrovascular disease were excluded from entering study 200952 .
 
Risk communication via guidance for investigators (see Section 6 of the IB) and informed consent form for subjects.

Hepatotoxicity	
Hepatotoxicity is an area of interest in drug development. Patients with T2DM are at increased risk for liver enzyme abnormalities and disease related liver conditions. One subject treated with albiglutide in the Phase III clinical program developed probable drug induced liver injury with an asymptomatic elevation in alanine amino transferase (ALT) and total bilirubin although the cases had some atypical features and complicating factors .
	
Routine liver safety laboratory evaluations will be conducted and specific withdrawal criteria for elevated liver function tests have been defined (See Section 5.4.1).

Investigational Product (IP) (albiglutide [GSK716155]) Additional Considerations		
Subject population with severe renal impairment (estimated glomerular filtration rate (eGFR) <30 mL/min/1.73m ²)	
Experience in T2DM subjects with severe renal impairment is limited (in the Phase III programme a total of 19 subjects with eGFR <30 mL/min/1.73m² received albiglutide).
 
In a Phase III study of patients with varying degrees of renal impairment, in the albiglutide group, on-therapy GI AEs occurred with a higher incidence and higher event rate in subjects with moderate and severe renal impairment
	
Subjects with an eGFR ≤30 mL/min/1.73 m² (calculated using the Modification of Diet in Renal Disease (MDRD) formula) are excluded from the study .
 
Risk communication via guidance for investigators (see Section 6 of the IB) and informed consent form for subjects.

Potential Risk of Clinical Significance	Summary of Data/Rationale for Risk	Mitigation Strategy
	
compared to those with mild renal impairment. GI events may lead to dehydration and worsen renal function.
	
Drug interactions	
Albiglutide causes a delay in gastric emptying, and thereby has the potential to impact the absorption of concomitantly administered oral medications.
 
During the development program, drug interactions studies were conducted with digoxin, warfarin, oral contraceptives, and simvastatin which demonstrated no clinically relevant PK or PD effects.
	
Investigators will be advised to take the effect of albiglutide on gastric emptying into account when prescribing concomitant medication.

Fetal & neonatal developmental toxicity	
Studies in animals have shown reproductive toxicity. The potential risk for humans is unknown. Albiglutide administration during the major period of organogenesis in female mice resulted in embryofetal lethality, and bent/wavy ribs in the fetus at 50 mg/kg/day.
 
Given that albiglutide is an albumin-based protein therapeutic, it is likely to be transferred to breast milk and may increase neonatal β-cell mass. Decreased body weight in offspring was observed in mice treated with albiglutide during gestation and lactation.
	
Subjects who are breastfeeding, pregnant or planning a pregnancy during the course of the study are excluded. Additionally, all females of child-bearing potential must be taking adequate contraception during the study and have a negative pregnancy test prior to entry. See Section 5.1 for further details.

Accelerated sexual maturation in juveniles	
Long-acting GLP-1R agonists have the potential to accelerate sexual maturation in monkeys based on absolute testes weight and similar trends in prostate, seminal vesicle, epididymides weights and histological assessment of maturity.
	
Subjects under 18 years of age were excluded from Study 200952.

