4.6.2. Benefit Assessment

In subjects with T2DM, treatment with albiglutide lyophilized drug product resulted in clinically relevant lowering of HbA_{1c} at both the 30 mg and 50 mg doses when given as monotherapy and in combination with metformin, sulfonylureas (SUs), thiazolidinedione or basal insulin. The durability of the effect on glycemic control was shown over a study period of up to 3 years. Consistent with its mechanism of action, albiglutide was not associated with clinically relevant hypoglycemia except when used in combination with an SU or insulin, and incidence rates with the combination were less than those reported with SUs or insulin alone. Body weight decreased slightly or remained stable during treatment, which is of benefit considering that continuous weight gain is a clinical problem in this patient group. Maintaining body weight while decreasing HbA_{1c} is therefore considered a beneficial effect of importance.

There are currently no data available for the use of the albiglutide liquid drug product in humans. Based on the current understanding of albiglutide degradation pathways and clinical outcomes from exposure to variants/impurities, similar PK, PD and clinical comparability between the liquid drug product and lyophilized drug product is expected.

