5.2. Exclusion Criteria

A subject will not be eligible for inclusion in this study if any of the following criteria apply:

[1] TYPE OF SUBJECT

1. Subject meets one or more of the withdrawal stopping criteria at Visit 1 (Week 26) (see Section [5.4](#))

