5.4. Withdrawal/Stopping Criteria

Every effort should be made to keep subjects in the study. The reason for a subject not completing the study will be recorded in the subject's electronic case report form (eCRF).

Any subject experiencing the following will be required to discontinue investigational product and will be withdrawn from the study:

- Any AE, which, in the opinion of the investigator precludes effective participation of the subject or poses a safety concern
- The following AEs **will** require withdrawal:
 - Confirmed pancreatitis, acute or chronic.
 - Pancreatic cancer.
 - Confirmed MTC or other thyroid C-cell neoplasia.
 - Liver chemistry abnormalities exceeding the threshold criteria outlined in Section [5.4.1](#)
 - QTc abnormalities exceeding the threshold criteria outlined in Section [5.4.2](#).
 - Severe allergic/hypersensitivity reactions that are considered by the investigator to be attributable to investigational product or without a likely alternative aetiology.
- eGFR ≤ 30 mL/min/1.73 m² (calculated using the MDRD formula).
- Subject becomes pregnant or intends to become pregnant during the study.
- Need for chronic use of a prohibited concomitant medication (Section [6.10.2](#))
- Major protocol deviation (the investigator should discuss the protocol deviation with the medical monitor before withdrawing study medication)
- Subject decision (reason to be documented in the eCRF, if specified by the subject)
- Investigator discretion
- Study closed/terminated or investigator site closed (where subject transfer to another site is not possible)

The following actions must be taken in relation to a subject who fails to attend the clinic for a required study visit:

- The site must attempt to contact the subject and re-schedule the missed visit as soon as possible.
- The site must counsel the subject on the importance of maintaining the assigned visit schedule and ascertain whether or not the subject wishes to and/or should continue in the study.
- In cases where the subject is deemed 'lost to follow up', the investigator or designee must make every effort to regain contact with the subject (where possible, 3 telephone calls and if necessary a certified letter to the subject's last known mailing address or local equivalent methods). These contact attempts should be documented in the subject's medical record.

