6.10. Concomitant Medications and Non-Drug Therapies

All medications taken at any time from Visit 1 (Week 26) to the follow-up visit will be recorded in the eCRF. The minimum requirement is that drug name and the dates of administration are to be recorded.

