6.10.1. Permitted Medications and Non-Drug Therapies

Unless specified as a prohibited medication in Section 6.10.2, all concomitant medications should be considered permitted provided they are not contraindicated in the albiglutide Prescribing Information or for the individual subject concerned. Although stable doses of all concomitant medications are preferable, changes in medications during the study to appropriately treat clinical conditions that might arise are allowed.

Like other members of the class, albiglutide causes a delay in gastric emptying, and thereby has the potential to impact the absorption of concomitantly administered oral medications. This should be taken into account by investigators when prescribing concomitant medication.

Investigators must adhere to the local labeling of the respective country (e.g., the Summary of Product Characteristics (SmPC) in relevant European countries or the FDA-approved prescribing information) for all permitted medications.

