6.10.2. Prohibited Medications and Non-Drug Therapies

Subjects must not use any of the following medications:

- Dipeptidyl peptidase-IV inhibitors and GLP-1R agonists (except albiglutide liquid drug product taken as study treatment) are prohibited.
- Any investigational drug other than study treatment (albiglutide liquid drug product).
- Oral or systemically injected corticosteroids (inhaled, intra-articular, epidural, and topical corticosteroids are allowed); short courses of oral steroids (single dose or multiple doses for up to 7 days) may be permitted provided these cases are discussed with the medical monitor

If a subject receives a prohibited medication, a protocol deviation will be reported and continuation in the study will be discussed with and agreed upon by the medical monitor.

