9.4. Key Elements of Analysis Plan

9.4.1. Primary Analyses

The overall general safety and tolerability of albiglutide liquid drug product will be evaluated in tabular and/or graphical format and summarized descriptively.

AEs and SAEs, physical examinations, clinical laboratory evaluations, vital sign measurements, and 12-lead electrocardiogram will be summarized. For continuous variables, these summaries will include sample size, mean, median, standard deviation (and/or standard error), minimum, and maximum. For categorical variables, the summaries will include frequencies and corresponding percentages. The exposure-adjusted incidence rate will also be calculated as the number of events in a given period divided by the total person time on treatment of subjects at risk within the same period. The exposure-adjusted incidence rate will be expressed as an annualized rate expected. No inferential testing will be performed on the safety variables. Hypoglycemic events will be analyzed separately from other AEs. All hypoglycemic events will be classified as severe, documented symptomatic, asymptomatic, probable symptomatic, and pseudohypoglycemia, as defined in Section [7.3.9](#).

AEs will be coded using MedDRA. AEs will be summarized in various subsets, including on therapy AEs, related AEs, AEs leading to treatment discontinuation or withdrawal from study, SAEs, fatal AEs, etc. AEs will also be summarized by maximum intensity (mild, moderate, and severe).

The evaluation of the safety and tolerability as assessed by immunogenicity of albiglutide liquid drug product will be provided by reporting descriptive statistics.

Anti-albiglutide antibody results will be summarized. In addition, the number and percentage of subjects with positive results along with the antibody titer values will be provided by visit.

Summary data for the primary analyses will be presented by visit and by subjects who needed hyperglycemic rescue during Study 200952 (at visit 1 of the current study), by subjects who did not need hyperglycaemic rescue during study 200952, and overall.

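### The protocol's hypoglycemia safeguard bars insulin and insulin secretagogues outside rescue, but its concomitant-medication rules permit them

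*Protocol*

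**What the plan says.** The hypoglycemia row of Table 2 (Protocol Section 4.6.1) gives this mitigation: "Subjects are neither allowed to use insulin nor insulin secretagogues during the study. Except as part of hyperglycemia rescue (see Section 5.3".

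The operative medication rules are in Section 6.10. Section 6.10.1 sets the default: "Unless specified as a prohibited medication in Section 6.10.2, all concomitant medications should be considered permitted", with a proviso for contraindicated drugs. Section 6.10.2 then lists three groups:

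1. DPP-IV inhibitors and GLP-1 receptor agonists other than study treatment
2. other investigational drugs
3. oral or systemically injected corticosteroids, with exceptions

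Two consequences attach to prohibited status. Section 6.10.2 states "If a subject receives a prohibited medication, a protocol deviation will be reported". Section 5.4 makes "Need for chronic use of a prohibited concomitant medication" a reason for withdrawal and cites 6.10.2. Section 5.2 carries the Section 5.4 criteria into eligibility by excluding anyone for whom "Subject meets one or more of the withdrawal stopping criteria at Visit 1 (Week 26" applies.

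Section 9.4.1 plans summaries "by subjects who needed hyperglycemic rescue during Study 200952 (at visit 1 of the current study"), and Section 9.4.2 uses the same split.

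**The concern.** A site that reads Table 2 learns that it may not start a sulfonylurea or insulin outside rescue. A site that reads Section 6.10, where one normally looks for medication rules, learns that it may.

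The drugs at issue are the ones the protocol itself links to the risk. Section 4.6.2 says "albiglutide was not associated with clinically relevant hypoglycemia except when used in combination with an SU or insulin". Hypoglycemia is an adverse event of special interest (Section 7.3.1.5) and is analyzed separately within the primary safety analyses (Section 9.4.1). At stake are how consistently sites apply a stated safeguard and what gets reported as a medication deviation.

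A related gap concerns subjects rescued in Study 200952. The analysis sections expect them to enter the extension, but the protocol does not say whether they may stay on insulin or a secretagogue started there.

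**Working it through.** The point rests on no statistical figure, so the check is a comparison of the sections.

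| Question | Table 2 (4.6.1) | Sections 6.10.1 and 6.10.2 |
|---|---|---|
| Insulin or secretagogue as rescue under 5.3 | Allowed | Allowed (not listed) |
| Insulin or secretagogue outside rescue | Not allowed | Permitted, unless contraindicated |
| Specific deviation rule (6.10.2) | – | Does not clearly apply (drug not listed) |
| Specific withdrawal rule (5.4) | – | Does not clearly apply (5.4 cites 6.10.2) |

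**Does any entry in 6.10.2 cover the drugs?** No: 0 of 3. The incretin entry names two classes only. It does not reach insulin, sulfonylureas or glinides, and there is no general secretagogue class.

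**Does the contraindication proviso close the gap?** The prescribing information is not in the document, so this cannot be settled directly. However, Section 4.6 describes Phase III experience on a background of basal insulin, and Section 4.6.2 reports benefit in combination with sulfonylureas or basal insulin. The protocol gives no sign of a contraindication.

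**Does Section 5.3 supply the ban?** No. It governs rescue and is silent on non-rescue use. It bars DPP-IV inhibitors and other GLP-1 analogues as rescue drugs, and those classes also appear in 6.10.2. The insulin and secretagogue ban was not carried across in the same way.

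**A concrete case.** A subject without symptoms of hyperglycemia has an HbA1c below the 8.5% rescue threshold in Table 3, and the investigator adds a sulfonylurea to tighten control. Section 6.10.1 permits this; Table 2 forbids it.

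**Carry-over.** The exception in Table 2 points only to Section 5.3, whose Table 3 sets rescue conditions for Weeks 26 to 52 of treatment. Neither addresses rescue therapy begun in Study 200952. Adding insulin and secretagogues to 6.10.2 without comment would act through the chain 6.10.2 → 5.4 (chronic need for a prohibited drug) → 5.2 (withdrawal criteria applied at Visit 1). It could then exclude subjects on long-term insulin or a secretagogue from earlier rescue, part of a group that 9.4.1 and 9.4.2 plan to summarize.

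**Scope.** At most 300 subjects × 26/52 years = 150 person-years of treatment fall under the conflicting rules. This is the whole planned exposure, not an estimate of time on the disputed drugs.

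**The case against.** The strongest reply is that the practical gap is narrow. Rescue under Section 5.3 is broad: an HbA1c threshold, timing left open, and investigator judgment for significant hyperglycemia. Insulin is the preferred add-on there and other drugs are discretionary. Most starts of insulin or a sulfonylurea for real hyperglycemia would therefore be allowed under either section, which leaves elective intensification and other non-rescue use.

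Other text also points to the intent of Table 2. Section 4.1 describes background therapy as diet and exercise or stable metformin, and Section 6.3 provides for adjusting metformin only. Section 4.6.1 presents Table 2 as summarizing mitigations that the protocol contains, so a breach could still be handled as a major deviation or under investigator discretion in Section 5.4. The study is single-arm and descriptive, no population defined in Section 9.3.1 depends on the prohibited list, and use can be traced because "All medications taken at any time from Visit 1 (Week 26) to the follow-up visit will be recorded in the eCRF".

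On carry-over, Table 3 says when a subject qualifies for rescue, not that earlier rescue therapy must stop. How those subjects were treated depends on the Study 200952 protocol, which is not at hand.

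Most of this stands as a limit on the consequences. It does not reconcile the sections. The metformin text supports the intent of Table 2 but does not override an explicit default that names 6.10.2 as the controlling list. The general routes in 5.4 rely on a site or monitor noticing the conflict. The carry-over point stands as an unanswered question, not as proof that such subjects would be mishandled.

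**Conclusion.** The contradiction is real and lies in the current text. As written, the operative medication rules permit what the hypoglycemia mitigation forbids, and the specific deviation and withdrawal rules do not implement that mitigation.

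The effect is on conduct and on deviation reporting. The protocol gives no expected frequency of non-rescue use, so no bias in hypoglycemia rates or in the HbA1c and FPG summaries is claimed. The conclusion assumes that albiglutide's labeling does not itself contraindicate these drugs, which Sections 4.6 and 4.6.2 make likely. It is worth correcting because it concerns a safeguard against a risk the protocol names, and the correction costs very little.

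**What to change.** Add a fourth entry to Section 6.10.2, along these lines: *Insulin and insulin secretagogues, except as hyperglycemia rescue under Section 5.3.*

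In the same entry, state whether subjects rescued with these drugs in Study 200952 may continue them in the extension. This sentence is essential because of the link through Sections 5.4 and 5.2. If they may continue, say that such use is not a prohibited medication for Sections 5.2 and 5.4. If they may not, the subgroup planned in 9.4.1 and 9.4.2 needs to be reconsidered.

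Identify any use outside rescue from the drug names and dates already recorded under Section 6.10.

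If the sponsor does not intend the ban, correct Table 2 instead so that the sections agree.

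Cost: one line and one sentence, with no new data collection.
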